9.2 Auditing

The UNMC Fred & Pamela Buffett Cancer Center Scientific Review Committee (SRC) will review this protocol on at least an annual basis.

This study will undergo audit on at least a quarterly basis by the UNMC Fred & Pamela Buffett Cancer Center Audit Committee.

Detailed policy and procedures for this section may be reviewed at: http://www.unmc.edu/cancercenter/clinical/prms.html.

Section 10.0 Statistical Considerations

The phase IIa portion will further assess the safety and tolerability and allow a preliminary assessment of the efficacy of the novel combination to provide background for an appropriately powered phase II study. We plan to accrue 24 patients into the phase IIa portion at a micronized dose of 800 mg of umbralisib and 560 mg of ibrutinib. The assessment of toxicity and efficacy will be performed within the entire cohort. To consecutively monitor the safety primary endpoint in the phase IIa portion, we will employ a sequential probability stopping rule for the predefined portion of cycles 1-4. This stopping rule specifies that the study will be terminated if a cumulative toxicity event (CTE) occurs in: $\geq 2/\text{first } 4$; $\geq 4/\text{first } 8$; or if more than 12 patients when the last (24th) evaluable patient has completed the trial have any CTE. This rule has the following stopping probability:

True	5%	10%	15%	20%	25%	30%	35%	40%	50%
toxicity									
rate									
Stopping prob.	0.000	0.000	0.001	0.004	0.016	0.056	0.118	0.243	0.632

A CTE is defined as:

- Grade ≥ 3 non-hematologic (attributed to either or both study drugs)
- Grade 4 hematologic toxicities (attributed to either or both drugs) defined as:
 - Grade 4 thrombocytopenia (platelets < 25 K/μL)
 - o Grade 4 neutropenia (absolute neutrophil count (ANC) < 0.5)
- Grade 3 thrombocytopenia or neutropenia that results in a > 7 day delay in either drug.
- One week or greater delay in initiating any cycle day 1 due to continued drug-related toxicity.

If a patient has progression of disease or is removed from study not related to a CTE after completion of 2 cycles but less than 4 cycles the patient's safety evaluation will be included, but noted appropriately. If less than 2 cycles than the patient will not be included and noted, but will not be replaced. The stopping rule would be appropriately adjusted if this were to occur.

An efficacy-stopping rule is also in place for the combination. After testing the combination on 12 patients, the trial will be terminated if </= 1 patients respond. If the trial goes on to the second stage and not discontinued due to the CTE stopping rules prior to, a total of 24 patients will be studied. If the total number responding is less than or equal to five, the regimen will be rejected. This follows a Simon two-stage design for efficacy following a minimax design with the following parameters: overall response rate for a poor regimen of 0.01, overall response rate for a good regimen of 0.31, a type I error of 0.20 and power of 80%.

Efficacy measures which will be determined include ORR, TTR, DOR, and PFS. ORR is defined as the percentage of patients achieving a best response of CR/CR, PR at any disease assessment time point. TTR is defined as the time or number of cycles between study registration and documentation of first response (CR/Cru, or PR). DOR is defined as the time or number of cycles between documentation of first response and progression, change of therapy, death, or date of last contact (if still alive without progression). PFS is defined as the time between study registration and documented progression or death if no progression was observed.

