5.6.1 Definitions of Cumulative Toxicity Event (CTE)

For this protocol, cumulative toxicity event (CTE) will be defined as follows: an adverse event attributed (definitely, probably or possibly related) to the study treatment and meeting following criteria within cycles 1 to 4. AE grading and assignment of attribution require documentation by medical personnel who are directly involved in the clinical care of protocol subjects.

Toxicity	Definition					
Hematologic	Either:					
	1. Grade 4 hematologic toxicities (attributed to either or both drugs) defined as:					
	b. Grade 4 thrombocytopenia (platelets < 25 K/μL)					
	c. Grade 4 neutropenia (absolute neutrophil count (ANC) < 0.5)					
	2. Grade 3 thrombocytopenia or neutropenia that results in a > 7 day delay in either					
	drug.					
Non-hematologic	Either:					
_	1. ≥ Grade 3 as per NCI Common Terminology Criteria for Adverse Events v4.03*					
	(attributed to either or both study drugs).					
	2. One week or greater delay in initiating any cycle day 1 due to continued drug-					
	related toxicity.					

^{*}Grade 3 nausea, vomiting, or diarrhea with maximal supportive treatment(s) will be considered a CTE. Fatigue Grade >/= 3 considered to be due to treatment (definitely, probably, or possibly related) will be considered a CTE.

Patients should be assessed clinically for toxicity at each visit using the NCI CTCAE v4.03 (http://evs.nci.nih.gov/ftp1/CTCAE/CTCAE) grading scale. The study will be terminated if a cumulative toxicity event (CTE) occurs in: ≥2/first 4; ≥4/first 8; or if more than 12 patients when the last (24th) evaluable patient has completed UNMC IRB#345-16 Protocol Version 4.2 Dated 07Oct2019

cycle 4. If a patient has progression of disease or is removed from study not related to a CTE after completion of 2 cycles but less than 4 cycles the patients safety evaluation will be included, but noted appropriately. If the patient receives less than 2 cycles than the patient will not be included and noted, but will not be replaced.

Dosing will occur only if a patient's clinical assessment and laboratory test values are acceptable.

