⁷ The study will be terminated if a cumulative toxicity event (CTE) occurs in: ≥2/first 4; ≥4/first 8; or if more than 12 patients when the last (24th) evaluable patients has completed cycle 4. If a patient has progression of disease or is removed from study not related to a CTE after completion of 2 cycles but less than 4 cycles the patient's safety evaluation will be included, but noted appropriately. If less than 2 cycles than the patient will not be included and noted, but will not be replaced. The stopping rule would be appropriately adjusted if this were to occur.

Page 28 of 65

⁸ Optional biopsies obtained via US or CT guided biopsy of accessible lymph node: Day 0 (pre-treatment; core biopsy), day 8 (fine needle aspiration) and end of treatment (progressive disease or end of study treatment—1 year; core biopsy). At the discretion of the treating investigator, patient on non-coumadin based anticoagulation should have anticoagulant held for biopsy.

⁹Mandatory research peripheral blood samples will be collected in a 20 ml EDTA tube pretreatment (day of biopsy or initiation of treatment; (+/- 3 days)), day 8 (+/- 3 days), 1 month (+/- 3 days) and 10 mL at subsequent radiographic response assessments, after cycle 2, 4, 6, 9, and 12. (+/- 7 days). After Month 12, efficacy assessments should occur at the investigators discretion with 10mL EDTA peripheral blood samples obtained ONLY IF FEASIBLE.]

Section 8.0 Drug Formulation and Procurement:

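### The cumulative toxicity rule has no prespecified boundary between patient 8 and the final check on 24, although safety is said to be monitored consecutively

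*Combined protocol and SAP*

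**What the plan says.** Section 10.0 sets the sample size ("We plan to accrue 24 patients into the phase IIa portion") and describes the safety rule: "To consecutively monitor the safety primary endpoint in the phase IIa portion, we will employ a sequential probability stopping rule". The predefined window is cycles 1 to 4.

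The same three boundaries appear in Section 5.6.1, footnote 7 of Section 7.0 and Section 10.0, and there are no others. Footnote 7 gives them as "≥2/first 4; ≥4/first 8; or if more than 12 patients when the last (24th) evaluable patients has completed cycle 4". Section 5.6.1 also times the last check at cycle 4. Section 10.0 words it differently: "or if more than 12 patients when the last (24th) evaluable patient has completed the trial have any CTE".

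Section 10.0 then says "This rule has the following stopping probability" and prints a table: 0.004, 0.056, 0.243 and 0.632 at true rates of 20%, 30%, 40% and 50%. Patients with fewer than two cycles are left out and not replaced, and for that case the plan says only: "The stopping rule would be appropriately adjusted if this were to occur".

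Three other kinds of oversight apply. Section 5.5 promises continued review of serious adverse events and toxicity trends. Section 9.1.2 sends all events of grade 3 or above, and all serious events, to the data and safety monitoring committee. Section 10.0 has a futility stop if at most 1 of 12 patients responds. None of these carries a CTE boundary.

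**The concern.** Consecutive monitoring suggests a rule that can act as evidence builds up. This rule is silent from patient 9 until all 24 have been through the CTE window. Safety and tolerability is the primary objective, and Section 2.4 justifies the phase IIa design by toxicity that emerges after the first cycle. If a regimen with a high CTE rate passes the first eight patients by chance, no prespecified CTE count can stop the next 16 from being enrolled and treated through cycle 4. The decision then rests on judgement alone, in the part of the trial that holds most of the patients.

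**Working it through.** **Inputs.** N = 24. Boundaries are 2 or more of 4, 4 or more of 8, and 13 or more of 24 (Sections 5.6.1, 7.0, 10.0). True CTE rates p of 20% to 50% come from the printed table; 60% is added here as an assumption. Model: independent patients, all evaluable, each assessed before the next look. Write q = 1 − p.

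**Step 1: the plan's own table.**
- Stop at 4: 1 − q⁴ − 4pq³. At p = 0.4: 1 − 0.1296 − 0.3456 = 0.5248.
- Stop at 8: q⁴p⁴ + 4pq³(4p³q + p⁴). At p = 0.4: 0.1296 × 0.0256 + 0.3456 × 0.1792 = 0.0652.
- Stop at 24, by exact binomial recursion: 0.0117.
- Total at p = 0.4: 0.602.

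| True rate | By patient 8 | Added at 24 | Total | Printed |
|---|---|---|---|---|
| 20% | 0.193 | 0.000 | 0.193 | 0.004 |
| 30% | 0.385 | 0.001 | 0.386 | 0.056 |
| 40% | 0.590 | 0.012 | 0.602 | 0.243 |
| 50% | 0.770 | 0.035 | 0.805 | 0.632 |
| 60% | 0.897 | 0.045 | 0.942 | not given |

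The printed figures do not reproduce. The look at 4 alone gives 0.181, 0.348, 0.525 and 0.688 at 20% to 50%, already above the printed values. Unprinted extra looks cannot explain this, because adding looks only raises the probability.

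**Step 2: the gap.** Patients 9 to 24 are 16 of 24, or 66.7%. The chance of passing both early looks is 1 minus the second column: 0.410, 0.230 and 0.103 at 40%, 50% and 60%. Given a pass, the chance of a CTE-rule stop before patient 24 is 0.

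**Step 3: would acting on the 13th CTE at once close it?** A trial that passes patient 8 has at most 3 CTEs, so a 13th needs 10 more and cannot occur before patient 18. The unconditional chance of reaching it before patient 24 is 0.0064 at 40% and 0.0222 at 50%. Given a pass, that is 0.0064 / 0.410 = 0.016 and 0.0222 / 0.2305 = 0.096. It does little.

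**Step 4: extend the existing line.** 2 of 4 and 4 of 8 are both 50%. The same line gives 6 of 12, 8 of 16 and 10 of 20.

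| True rate | Stops at 12 + 16 + 20 | Given passing patient 8 | Overall stopping | Expected N |
|---|---|---|---|---|
| 20% | 0.003 | 0.4% | 0.193 → 0.196 | 20.20 → 20.16 |
| 30% | 0.021 | 3% | 0.386 → 0.405 | 16.45 → 16.25 |
| 40% | 0.0292 + 0.0166 + 0.0106 = 0.056 | 14% | 0.602 → 0.647 | 12.46 → 11.93 |
| 50% | 0.0396 + 0.0244 + 0.0169 = 0.081 | 35% | 0.805 → 0.852 | 8.94 → 8.20 |
| 60% | 0.0336 + 0.0190 + 0.0122 = 0.065 | 63% | 0.942 → 0.964 | 6.36 → 5.76 |

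The third column divides the stops by the probability of passing, for example 0.0564 / 0.410 = 0.138. Expected N is the sum of n × P(stop at n) plus 24 × P(no stop). Under the current rule at 40%: 4 × 0.5248 + 8 × 0.0652 + 24 × 0.410 = 12.46.

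Given a pass at patient 8, expected N falls from 24 to 22.7, 20.8 and 18.1 at 40%, 50% and 60%.

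**The case against.** The number of looks in a 24-patient study is a design choice, and the early looks do most of the work: they end 59% to 90% of trials at rates of 40% to 60%. The conditional gains apply only to the trials that continue, which are 41%, 23% and 10% of the total. Averaged over all trials the saving is under one patient. That stands, and it limits the size of the point.

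Three stronger readings are tempting but not supported.
- A reader might infer that the last check comes after all treatment has ended. Sections 5.6.1 and 7.0 place it at cycle 4, and Section 5.10.1 allows up to 12 cycles, so on that timing a stop could still affect up to 8 later cycles. Only the wording in Section 10.0 suggests otherwise.
- A reader might infer that patients 9 to 24 would be treated whatever happens. Trend review, committee reporting and the futility look at 12 all remain in force. What is missing is a prespecified CTE boundary.
- A reader might call the combination untested. The rationale for the combination (Section 2.3) reports 16 patients given both drugs with ublituximab, with no dose-limiting toxicity in the lymphoma cohorts. The doublet alone is what is new.

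The savings are also best-case. The window is four 28-day cycles and no accrual pause is described, so later patients may already be on treatment when a look completes. For the same reason the existing look at 8 may protect fewer patients than it appears to.

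**Conclusion.** The point holds in a limited form. The rule described as consecutive has no CTE boundary for 16 of the 24 patients, and the final check cannot spare them entry or cycles 1 to 4. In trials that pass patient 8, added looks on the plan's own 50% line raise the chance of stopping before patient 24 from 0 to 14%, 35% and 63% at true rates of 40%, 50% and 60%. The unconditional saving is 0.5 to 0.7 patients. This is a cheap improvement in protection rather than a flaw that invalidates the design.

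The figures assume independent patients, full evaluability and no overlap between accrual and assessment. Calling a stop at 20% or 30% false is also an assumption, since the plan names no acceptable CTE rate. All baseline figures are for the rule as printed. Because the printed table belongs to some other rule, the intended operating characteristics are unknown until the two are reconciled.

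**What to change.** 1. Reconcile the three printed boundaries with the printed stopping probabilities before anything else.
2. Add looks at 12 (6 or more), 16 (8 or more) and 20 (10 or more), and count each CTE when it occurs rather than when the patient's window closes.
3. Reconcile the timing of the last check (cycle 4 in 5.6.1 and 7.0, the trial in 10.0) and the CTE window (cycles 1 to 4 in 5.6.1 and 10.0, cycles 1 to 6 in 5.7).
4. State the boundaries that apply if fewer than 24 patients are evaluable, and say whether accrual continues while a look is pending.
5. Recompute the table for the final rule.

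No separate clause for a 13th CTE is needed. Passing patient 20 under the added looks means at most 9 CTEs, so 13 cannot be reached before patient 24.

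The cost is a sentence in each of Sections 5.6.1, 7.0 and 10.0 and a new table. The statistical price is a rise in stopping from 0.193 to 0.196 at a true rate of 20% and from 0.386 to 0.405 at 30%.

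### The last CTE stopping boundary (13 of 24, 54%) is looser than the first two (2 of 4 and 4 of 8, both 50%), and the plan gives no parameters or rounding convention that would explain it

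*Combined protocol and SAP*

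**What the plan says.** Section 10.0 names the method for the primary safety endpoint: "we will employ a sequential probability stopping rule for the predefined portion of cycles 1-4". It gives no null or alternative CTE rate, no error rates and no rounding convention for this rule. (The parameters later in that section belong to the separate Simon design for response.)

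The same three counts appear in three places. Section 5.6.1 has "The study will be terminated if a cumulative toxicity event (CTE) occurs in: ≥2/first 4; ≥4/first 8", followed by more than 12 patients at the 24th. Section 7.0 footnote 7 has "The study will be terminated if a cumulative toxicity event (CTE) occurs in: ≥2/first 4; ≥4/first 8; or if more than 12 patients". Section 10.0 ends the rule with "or if more than 12 patients when the last (24th) evaluable patient has completed the trial have any CTE".

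The timing of the last look differs. Footnote 7 sets it "or if more than 12 patients when the last (24th) evaluable patients has completed cycle 4", and Section 5.6.1 agrees, whereas Section 10.0 waits for completion of the trial.

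Section 10.0 then says "This rule has the following stopping probability" and prints values from 0.000 at a true rate of 5% to 0.632 at 50%. Patients with fewer than 2 cycles are excluded and not replaced; for that case the section says only: "The stopping rule would be appropriately adjusted if this were to occur".

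**The concern.** Evidence is weakest at 4 patients and strongest at 24, yet the observed rate needed to stop rises from 50% to 54%. Two CTEs in 4 patients (exact 95% interval 7% to 93%) end the study, while 12 in 24 (29% to 71%) do not. That is the reverse of what the named method does.

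The last count is the only part of the rule that uses CTE data from patients 9 to 24, so it decides the primary endpoint for any trial that gets past patient 8. A monitoring committee seeing 12 of 24 would have no stated reason why the same observed rate ended the study earlier but is acceptable now.

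**Working it through.** **Inputs.** Looks at 4, 8 and 24 patients; stop at 2, 4 and 13 CTEs (Sections 5.6.1, 7.0 footnote 7 and 10.0). Planned size: "We plan to accrue 24 patients into the phase IIa portion". I assume all 24 are evaluable, with independent CTEs at a constant rate p.

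**1. The plan's own table.** At p = 0.5, exact binomial calculation gives:

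- Look 1: P(X4 ≥ 2) = 1 − (1 + 4)/16 = 11/16 = 0.6875.
- Look 2: survivors have 0 CTEs (1/16) or 1 CTE (4/16). They stop with 4 of the next 4 (1/16) or at least 3 of the next 4 (5/16). Added stopping = 1/256 + 20/256 = 21/256 = 0.082; cumulative 0.770.
- Last look: 59/256 = 0.230 of trials remain, with 0, 1, 2 or 3 CTEs at probabilities 1, 8, 22 and 28 (each /256). Reaching 13 takes at least 13, 12, 11 or 10 of the next 16, with probabilities 0.0106, 0.0384, 0.1051 and 0.2272. Added stopping = (1×0.0106 + 8×0.0384 + 22×0.1051 + 28×0.2272)/256 = 0.035; total 0.805.

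The printed value is 0.632, below what the first look alone gives. The same recursion at every tabulated rate:

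| True rate | Printed | By patient 8 | Written rule (13) | With 12 |
|---|---|---|---|---|
| 5% | 0.000 | 0.014 | 0.014 | 0.014 |
| 10% | 0.000 | 0.053 | 0.053 | 0.053 |
| 15% | 0.001 | 0.114 | 0.114 | 0.114 |
| 20% | 0.004 | 0.193 | 0.193 | 0.193 |
| 25% | 0.016 | 0.284 | 0.285 | 0.286 |
| 30% | 0.056 | 0.385 | 0.386 | 0.390 |
| 35% | 0.118 | 0.488 | 0.493 | 0.503 |
| 40% | 0.243 | 0.590 | 0.602 | 0.621 |
| 50% | 0.632 | 0.770 | 0.805 | 0.836 |

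The table is not reproduced. A search over all counts at looks of 4, 8 and 24 found no rule matching every entry within 0.02. The closest was 4/4, 6/8, 12/24 (largest gap 0.034), and the other close fits also ended at 12.

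**2. Boundary as a proportion.** 2/4 = 50.0%; 4/8 = 50.0%; 13/24 = 54.2%.

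**3. What a sequential probability boundary allows.** The upper line is h + s·n, with h = ln((1 − β)/α)/k, s = ln((1 − p0)/(1 − p1))/k and k = ln[p1(1 − p0)/(p0(1 − p1))]. In any usable design h > 0, so the critical proportion s + h/n falls with n. Suppose stopping occurs at the first integer on or above the line:

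- Count 2 at n = 4 needs h + 4s ≤ 2. With h > 0, s < 0.5. Then h + 24s = (h + 4s) + 20s ≤ 2 + 20s < 12, so the count at 24 is at most 12.
- Count 4 at n = 8 needs h + 8s > 3. Subtracting h + 4s ≤ 2 gives 4s > 1, so s > 0.25. Then h + 24s = (h + 8s) + 16s > 3 + 4 = 7, so the count is at least 8.

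The range is 8 to 12. A grid over p0, p1, α and β returned the same counts and never 13.

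**4. Other rounding.** With p0 = 0.17, p1 = 0.84 and α = β = 0.20, the line is 2.46, 4.49 and 12.61; rounding to nearest gives 2, 4, 13. With p0 = 0.34, p1 = 0.67, α = 0.20 and β = 0.30, the line is about 2.93, 4.96 and 13.04; rounding down gives 2, 4, 13. In both, the line's own proportion still falls with n. The rise comes from rounding, which makes the early looks stop before the line is reached.

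**5. Size of the last look.** From the table, it adds 0.602 − 0.590 = 0.012 at 40% and 0.805 − 0.770 = 0.035 at 50%, the largest addition. Among trials reaching patient 24 it stops 0.012/0.410 = 2.9% and 0.035/0.230 = 15%. Using 12 adds at most 0.004 to overall stopping up to 30%, then 0.010 at 35%, 0.019 at 40% and 0.032 at 50%.

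**The case against.** Four points can be made for the plan.

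First, a reader might infer that no sequential probability rule could yield 2, 4 and 13. The documents do not support that: Section 10.0 states neither parameters nor rounding, and step 4 shows rules that give those counts. This objection stands. What remains is that 13 needs a rounding convention the plan does not state.

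Second, a reader might infer that a regimen with a true CTE rate of 50% passes. It does not: the written rule stops such a trial with probability 0.805. The anomaly concerns an observed 12 of 24 only.

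Third, strict early looks are a defensible choice for a new doublet, and the last look acts rarely mainly because those looks have already stopped most toxic trials. At that point accrual is complete, and on Section 10.0's timing treatment may be too. This limits the practical effect, but does not explain why the same observed rate is judged differently with more data.

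Fourth, the early counts may be the misprint. At 20% the first look alone stops with probability 0.181, against a printed total of 0.004. This stands, and argues against editing the last count in isolation.

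**Conclusion.** The concern holds in a limited form. The last boundary is looser than the two before it, in all three sections, and this departs from the named method under its usual convention of stopping on or above the line. It could arise from rounding, but the plan gives nothing from which to tell.

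The effect on overall stopping is small, at most 0.032 at the tabulated rates, so this is no large loss of safety protection. It merits correction because it is the decision threshold of the primary endpoint and is cheap to repair. The mismatch between the printed table and the written rule is much larger (0.056 printed against 0.386 at 30%) and means the three counts cannot be repaired one at a time.

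The probabilities assume 24 evaluable patients and looks only at 4, 8 and 24. The range of 8 to 12 also assumes that 2/4 and 4/8 are intended.

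**What to change.** State p0, p1, α, β and the rounding convention of the safety rule in Section 10.0. Derive all three counts from them so that the last boundary is no looser than the earlier ones. If 2/4 and 4/8 are kept, the smallest change is 12 or more of 24 in place of more than 12.

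Use identical counts in Sections 5.6.1, 7.0 (footnote 7) and 10.0, reconcile the timing of the last look across them, and say how the counts change when patients are not evaluable. Then recompute the stopping-probability table. For 2/4, 4/8 and 12/24 the entries are those in the last column above.

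The cost is an edit in three places and a recalculated table. The downside of 12 is a slightly higher chance of stopping: at most 0.4 percentage points at true rates up to 30%.

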Fatal bleeding events have occurred in patients treated with ibrutinib. Grade 3 or higher bleeding events (subdural hematoma, gastrointestinal bleeding, hematuria and post procedural hemorrhage) have occurred in up to 6% of patients. Bleeding events of any grade, including bruising and petechiae, occurred in approximately half of patients treated with ibrutinib.

The mechanism for the bleeding events is not well understood.

Ibrutinib may increase the risk of hemorrhage in patients receiving antiplatelet or anticoagulant therapies.

Consider the benefit-risk of withholding ibrutinib for at least 3 to 7 days pre and post-surgery depending upon the type of surgery and the risk of bleeding.

Infections

Fatal and non-fatal infections have occurred with ibrutinib therapy. Grade 3 or greater infections occurred in 14% to 26% of patients. Cases of progressive multifocal leukoencephalopathy (PML) have occurred in patients treated with ibrutinib. Monitor patients for fever and infections and evaluate promptly.

A rare and usually fatal viral disease in the brain, Progressive Multifocal Leukoencephalopathy (PML), has been reported in patients treated with ibrutinib in combination with rituximab and in patients who were previously treated with rituximab.

Cytopenias

Treatment-emergent Grade 3 or 4 cytopenias including neutropenia (range, 19 to 29%), thrombocytopenia (range, 5 to 17%), and anemia (range, 0 to 9%) occurred in patients treated with ibrutinib. Monitor complete blood counts monthly.

Atrial Fibrillation

Atrial fibrillation and atrial flutter (range, 6 to 9%) have occurred in patients treated with ibrutinib, particularly in patients with cardiac risk factors, acute infections, and a previous history of atrial fibrillation. Periodically monitor patients clinically for atrial fibrillation. Patients who develop arrhythmic symptoms (e.g., palpitations, lightheadedness) or new onset dyspnea should have an ECG performed. If atrial fibrillation persists, consider the risks and benefits of ibrutinib treatment and dose modification.

Hypertension

Hypertension (range, 6 to 17%) has occurred in patients treated with ibrutinib with a median time to onset of 4.5 months (rang, 0.03 to 18.40 months). Monitor patients for new onset hypertension or hypertension that is not UNMC IRB#345-16 Protocol Version 4.2 Dated 07Oct2019

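### The stopping probabilities printed for the CTE rule cannot come from that rule: at 20-30% true toxicity it stops the trial with probability 0.19-0.39, not 0.004-0.056

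*Combined protocol and SAP*

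**What the plan says.** Section 10.0 describes the monitoring of the primary endpoint: "we will employ a sequential probability stopping rule for the predefined portion of cycles 1-4". It sets the sample size ("We plan to accrue 24 patients into the phase IIa portion") and pools the three groups: "The assessment of toxicity and efficacy will be performed within the entire cohort". The boundaries appear in three places with the same numbers:

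- Section 5.6.1: "The study will be terminated if a cumulative toxicity event (CTE) occurs in: ≥2/first 4; ≥4/first 8; or if more than 12 patients".
- Section 7.0, footnote 7: "≥2/first 4; ≥4/first 8; or if more than 12 patients when the last (24th) evaluable patients has completed cycle 4".
- Section 10.0: the same limits at 4 and 8 patients, then "or if more than 12 patients when the last (24th) evaluable patient has completed the trial have any CTE".

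After the boundaries, Section 10.0 says "This rule has the following stopping probability" and gives nine values for true toxicity rates of 5, 10, 15, 20, 25, 30, 35, 40 and 50%: 0.000, 0.000, 0.001, 0.004, 0.016, 0.056, 0.118, 0.243 and 0.632.

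**The concern.** Two events among four patients are not rare at moderate toxicity rates, so a rule that stops on 2 of 4 cannot have a stopping probability near zero at 20%. The printed row has the shape of a much more permissive rule.

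Safety and tolerability is the primary objective, and this row is the only statement of how the safety rule behaves. Anyone approving the design from it would conclude that a regimen with a 20% CTE rate has a 0.4% chance of being terminated, and one with a 30% rate a 5.6% chance. If those figures are wrong, the design was assessed on a false premise. An early stop would also look like much stronger evidence of excess toxicity than it is.

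**Working it through.** **Inputs.** Boundaries of at least 2/4, at least 4/8 and more than 12 (that is, at least 13) of 24, from Sections 5.6.1, 7.0 and 10.0. The true rates and stated probabilities come from the table in Section 10.0. Patients are taken as independent with a common CTE probability p, and the looks are counted among evaluable patients.

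**Step 1: lower bound from the first look.** The whole rule cannot stop less often than its first look, for which

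P(X ≥ 2 | n = 4) = 1 − (1−p)^4 − 4p(1−p)^3.

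- p = 0.20: 1 − 0.4096 − 0.4096 = 0.1808 (stated total 0.004).
- p = 0.30: 1 − 0.2401 − 0.4116 = 0.3483 (stated 0.056).
- p = 0.50: 1 − 0.0625 − 0.2500 = 0.6875 (stated 0.632).

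**Step 2: second look.** A trial that passes the first look has 0 or 1 events. It stops at 8 patients if the next four bring the total to at least 4:

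(1−p)^4 · p^4 + 4p(1−p)^3 · [4p^3(1−p) + p^4].

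- p = 0.20: 0.4096 × 0.0016 + 0.4096 × 0.0272 = 0.0118.
- p = 0.30: 0.2401 × 0.0081 + 0.4116 × 0.0837 = 0.0364.

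**Step 3: full rule.** Carrying the surviving event counts forward to 24 patients and stopping at 13 or more gives:

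| True rate | Stated | Look at 4 | Look at 8 | Look at 24 | Exact total |
|---|---|---|---|---|---|
| 5% | 0.000 | 0.0140 | 0.0001 | 0.0000 | 0.014 |
| 10% | 0.000 | 0.0523 | 0.0011 | 0.0000 | 0.053 |
| 15% | 0.001 | 0.1095 | 0.0047 | 0.0000 | 0.114 |
| 20% | 0.004 | 0.1808 | 0.0118 | 0.0000 | 0.193 |
| 25% | 0.016 | 0.2617 | 0.0227 | 0.0003 | 0.285 |
| 30% | 0.056 | 0.3483 | 0.0364 | 0.0013 | 0.386 |
| 35% | 0.118 | 0.4370 | 0.0513 | 0.0046 | 0.493 |
| 40% | 0.243 | 0.5248 | 0.0652 | 0.0117 | 0.602 |
| 50% | 0.632 | 0.6875 | 0.0820 | 0.0351 | 0.805 |

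A simulation of 400,000 trials per rate gave 0.193, 0.286 and 0.385 at 20, 25 and 30%. The stated row is not reproduced at any rate, and the look-at-4 column alone exceeds it throughout. The largest gap is at 35%: 0.493 − 0.118 = 0.375.

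**Step 4: other readings.**

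| Reading | 20% | 30% | 50% |
|---|---|---|---|
| Stated | 0.004 | 0.056 | 0.632 |
| Strict inequality at every look (>2/4, >4/8, >12/24) | 0.032 | 0.114 | 0.587 |
| Looks at 8 and 24 only | 0.056 | 0.196 | 0.699 |
| More than 12 of 24 only | 0.000 | 0.012 | 0.419 |
| At least 12 of 24 only | 0.001 | 0.031 | 0.581 |
| All three boundaries required together | 0.000 | 0.008 | 0.321 |

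None matches. With 18, 20 or 22 evaluable patients the 20-30% values of the written rule change by about 0.001 at most. Among alternative boundaries at 4, 8 and 24 patients, the closest (4/4, 6/8, 12/24) still misses by up to 0.034. The documents do not say how the row was produced, so its source cannot be identified.

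**The case against.** The best reply concedes the arithmetic and argues about consequences.

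- **Boundaries govern conduct.** The boundaries decide what happens, not the table. They are printed openly three times, so any reader can see that two events in four patients end the study. This is true, but it does not make the printed probabilities correct, and nobody can judge whether the boundaries are acceptable from figures that belong to some other rule.
- **The error is protective.** The rule stops more readily than stated, so the misstatement does not expose patients to more toxicity than the boundaries allow. This stands. The cost is an understated chance of losing the trial early, not a gap in protection. If the printed row was the intended behaviour, however, the boundaries in all three sections are the mistake.
- **No acceptable CTE rate is defined.** This also stands: calling a stop at 20% a false stop would be the reader's judgement. The discrepancy exists at all nine rates and does not depend on that label. A rate of 20-40% for the doublet is an assumption. Section 8.5 reports for ibrutinib that "Grade 3 or greater infections occurred in 14% to 26% of patients", which is indirect support at best, because a CTE must be attributed to study treatment and fall within cycles 1-4.
- **Four patients is loose.** Section 10.0 describes no accrual pause, and the CTE window is four 28-day cycles. More than four patients may therefore be enrolled when the first look is decided. This affects how many are treated before a stop, not the probability of stopping.

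**Conclusion.** The rule and its published properties cannot both be right. Under the written boundaries the stopping probability is 0.193 rather than 0.004 at 20% (about 48-fold), 0.285 rather than 0.016 at 25% (about 18-fold), 0.386 rather than 0.056 at 30% (about 7-fold), and 0.805 rather than 0.632 at 50%. Most of it arises at the first look: 0.1808/0.1926 = 94% at 20% and 0.3483/0.3860 = 90% at 30%.

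The exact values assume independent patients with a common CTE rate. The conclusion does not depend on how the final look is read or on modest numbers of unevaluable patients, because the first look alone already exceeds every printed value. This must be corrected, since it is the only operating characteristic given for the primary endpoint. The documents do not show whether the boundaries or the row was intended.

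**What to change.** The sponsor should first state which of the two was intended.

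- **If the boundaries:** replace the row in Section 10.0 by 0.014, 0.053, 0.114, 0.193, 0.285, 0.386, 0.493, 0.602 and 0.805, and confirm that these properties are acceptable.
- **If the row:** re-derive the boundaries by exact enumeration until rule and table agree, and carry the new boundaries into Sections 5.6.1, 7.0 and 10.0.

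In either case, state the calculation method and assumptions beside the table. Reconcile the timing of the final look as well: Sections 5.6.1 and 7.0 place it when the 24th evaluable patient finishes cycle 4, Section 10.0 when that patient finishes the trial.

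The cost is an exact binomial calculation and one table row, or new boundaries in three sections. No patients are added to the plan. If the boundaries are kept, the stated chance of early termination becomes visibly less favourable.
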